12.2 STATISTICAL ANALYSIS PLAN

A full Statistical Analysis Plan (SAP) will be drafted in accordance with the KCTU Standard Operating Procedures authored and approved by the Trial Steering Committee and Data Monitoring and Ethics Committee.

The Junior Trial Statistician will be fully blind until the first version of the SAP is approved by the Data Monitoring Committee (DMC).

After the first version of the SAP is approved by the DMC, the Junior Trial Statistician will become unblinded and access participant level data by arm. The Junior Statistician will then have access to the adherence data and be able to monitor and inform the DMC of the trial adherence of the participants. They will present the closed DMC report to the DMC members.

The Junior Trial Statistician will not take part in any discussion that influences the early stopping of the trial at any TMG, TSC, or DMC meetings.

12.3 **GENERAL PRINCIPLES**

We will report data in line with the Consolidated Standards of Reporting Trials (CONSORT) for multiarm trials showing attrition rates and loss to follow-up. This will include the number of eligible patients, number of patients agreeing to enter the trial, number of patients refusing, then by intervention arm: the number of patients compliant/non-compliant with treatment, the number continuing through the trial, the number withdrawing, the number lost to follow-up and the numbers excluded/analysed at each time point.

Analyses will be carried out using the intention to treat principle: participants will be analysed in the group they are randomised to, and available data from all participants are included, including those who do not complete therapy. Every effort will be made to follow up all participants in all arms for research assessments. For estimates of treatment effects in each comparison, only participants who could have been randomised to either arm (i.e. not contraindicated to either drug and contemporaneously randomised) will be included in that comparison.

Analysis will be conducted in Stata version 17.0 or later.

12.4 **BASELINE CHARACTERISTICS**

No statistical significance tests or confidence intervals will be calculated for the difference between randomised groups on any participant level baseline variables. The randomisation of participants to intervention groups means that any imbalance over all measured and unmeasured baseline characteristics is by definition due to chance.

Appropriate summary statistics will be applied to describe demographic and clinical measures: mean and standard deviation for all symmetric (non-skewed) distributed measures; median, 25th and 75th

quartiles for skewed distributions. QQ plots and histograms will be used to assess data distributions of continuous measures. Categorical outcomes will be described using both numbers and proportions (percentage).

12.5 STATISTICAL METHODS FOR PRIMARY AND SECONDARY OUTCOMES

12.5.1 STATISTICAL METHODS FOR PRIMARY OUTCOME

For the repeated measures of the continuous EASI score, linear mixed models will be fitted to the outcome variable at all time points. We will use a linear mixed model, with fixed effects of trial arm, time and a time*arm interaction term, baseline values of the EASI score and minimisation factors (recruitment centre, severity). Random intercepts will be fitted at the participant level.

Marginal treatment effects will be estimated for the EASI score at 6 months and reported as adjusted mean difference in scores between the comparative groups, its standard error, 97.5% confidence intervals and p-value. Significance level (type 1 error) will be two-sided at 0.025.

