12 STATISTICAL METHODS

12.1 SAMPLE SIZE JUSTIFICATION

This study is designed to test separate pair-wise comparisons of methotrexate, dupilumab and abrocitinib for superiority against ciclosporin. The minimum clinically important difference for EASI is 6.6³⁷. In order to detect a mean absolute difference of 6.6 (assuming a standard deviation of 13.6

(pooled SD=13.6 for EASI at 24 weeks in the pivotal industry trial LIBERTY AD CHRONOS⁹), 20% loss to follow up at primary endpoint, with 90% power and conservative type 1 error rate of 2.5% per comparison) we will need to randomise at least 134 participants per arm. This will have 94% power to test a difference between each comparator and ciclosporin of 6.6 on EASI, 90% for a difference of 6 points, and 80% for 5.2 points. In the subgroup of ~30% participants with severe disease at baseline (n=40 per arm), there is 80% power for a difference of 9.6 points and 50% power for 6.6 points. In order to enable a powered comparison between new arms (e.g. abrocitinib) and the current control arm (ciclosporin) using contemporaneously recruited participants, we will need to extend recruitment to the current control arm.

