12.10 METHODS TO HANDLE MISSING DATA

For missing outcome data, the results from the linear mixed models are valid under a missing at random (MAR) missing data generating mechanism that allows for fixed effects and earlier outcome values to predict missingness of later ones.

Considering incomplete baseline measures: although baseline data should be complete prior to randomisation, there may be some limited missing data. Descriptive baseline summaries will be presented as complete case. The proportion of missing data will be summarised by scale/assessment. If any of the baseline measures are found to relate to missing primary outcome at 6 months we will consider adjusting for them in models for the primary outcome. To allow for this, any baseline measure considered as a covariate in the main model would best be imputed to a full single dataset. Missing baseline covariate data will therefore be imputed using the missing indicator method where a dummy variable for missingness will be included as a covariate in the model for binary data, and mean imputation for continuous data, as per the recommendations of White and Thompson (2005).

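### The only covariance term stated for the primary model is a participant random intercept, so the month-6 confidence interval and 0.025 test rest on a variance pooled over five visits, two of them after the treatment switch

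*Protocol*

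**What the plan says.** In section 12.5.1, "linear mixed models will be fitted to the outcome variable at all time points". The fixed effects are arm, time, their interaction, baseline EASI, centre and severity. The covariance is described in one sentence: "Random intercepts will be fitted at the participant level". The month-6 adjusted difference, its standard error, the 97.5% interval and the p-value all come from this model, and "Significance level (type 1 error) will be two-sided at 0.025". The protocol mentions no visit-specific variance, unstructured covariance or robust standard error.

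Section 4.2 and Table 1 place post-baseline EASI at months 1, 3, 6, 9 and 12. Section 2 has non-responders switch drug at month 6, so two of the five visits follow the switch. Section 12.10 relies on the same models for missing outcomes: "the results from the linear mixed models are valid under a missing at random (MAR) missing data generating mechanism". Section 12.5.2 carries the approach over to the continuous secondary outcomes.

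**The concern.** A lone random intercept with independent, equal-variance residuals makes every visit equally variable and every pair of visits equally correlated. The standard error of a month-6 contrast then reflects the average spread over the year, not the spread at month 6.

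The design gives reason to doubt that these are equal. Some arms may increase dose at month 3. Participants who fail the response criteria, which are partly EASI-based, change drug at month 6, or are withdrawn if the switch is not possible (section 5.3.3). Both can alter the spread at months 9 and 12 and its correlation with month 6.

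At stake is the stated error rate of each primary comparison. Section 17.1 also relies on the 0.025 level being conservative when it argues that no further multiplicity control is needed.

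**Working it through.** **Inputs from the protocol.** Two-sided level 0.025 (12.5.1); difference 6.6 and "pooled SD=13.6 for EASI at 24 weeks" (12.1); "20% loss to follow up at primary endpoint" (12.1); visits at months 1, 3, 6, 9 and 12 (4.2). SDs at the other visits are not given and are assumed below.

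**The plan's own figure.** n per arm = 2 × (2.2414 + 1.2816)² × 13.6² / 6.6² = 2 × 12.41 × 184.96 / 43.56 = 105.4, so 106 evaluable. The t-based version needs 107, and 107 / 0.8 = 133.75, so 134, as stated. The sample size thus uses the 24-week SD alone, whereas the analysis model would use a variance pooled over the year.

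**Formula.** With complete data and a saturated arm-by-time mean, the random-intercept model gives month-6 SE = √(mean of the five visit variances × 2/n). The correct SE uses the month-6 variance, 13.6² = 184.96. With r = √(mean variance / 184.96), the actual two-sided level is 2 × [1 − Φ(2.2414 × r)]. Only the ratio of variances matters, so baseline adjustment leaves the result unchanged if it shrinks all visits equally.

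**Example.** SDs 13.6/13.6/13.6/10/10: mean variance = (3 × 184.96 + 2 × 100) / 5 = 150.98; r = √(150.98 / 184.96) = 0.903; 2.2414 × 0.903 = 2.025; level 4.3%.

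| Assumed SD, months 1/3/6/9/12 | Mean variance | r | Level by formula | Level simulated |
|---|---|---|---|---|
| 17/15/13.6/13.6/13.6 | 213.78 | 1.075 | 1.6% | 1.6% |
| 16/14.5/13.6/12.5/12 | 190.29 | 1.014 | 2.3% | 2.4% |
| 13.6 throughout | 184.96 | 1.000 | 2.5% | 3.0% |
| 16/14.5/13.6/10/10 | 170.24 | 0.959 | 3.2% | 2.8% |
| 13.6/13.6/13.6/10/10 | 150.98 | 0.903 | 4.3% | 4.1% |
| 12/12.5/13.6/10.5/9.5 | 137.14 | 0.861 | 5.4% | 6.4% |
| 10.9/10.9/13.6/10.9/10.9 | 132.04 | 0.845 | 5.8% | 5.9% |

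**Simulation.** Null effect, 134 per arm, random dropout reaching 20% at month 6, arm-by-visit means plus baseline EASI, REML random intercept. Runs: 9,000 (Monte Carlo SE about 0.2 points), except 3,000 for 16/14.5/13.6/10/10. The 12/12.5/13.6/10.5/9.5 row comes from a separate simulation. Centre and severity were left out. The excess in the equal-SD row arises because the assumed correlation with baseline falls over visits while the model has one common baseline slope.

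Mean model SE against actual SE at month 6:
- narrowing after the switch (13.6/13.6/13.6/10/10): 1.58 against 1.74
- other visits at about 0.8 of the month-6 SD: 1.46 against 1.74
- wider early visits (17/15/13.6/13.6/13.6): 1.87 against 1.75

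**Remedies in the same simulations.**
- Participant-clustered robust SE on the same model: 2.4% to 2.9%.
- Month-6 ANCOVA, which an unstructured model with a baseline-by-visit term reproduces when data are complete: 2.3% to 2.8%.
- Dropping months 9 and 12 but keeping the lone random intercept: 3.5% (narrowing after the switch) and 2.1% (wider early visits), 5,000 runs each. This alone is not a full cure.

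**Missing data.** In one constructed scenario, with roughly 20% dropout depending on month-3 EASI and stronger in one arm, the random-intercept estimate was biased by −0.24 EASI points, against −0.01 for an unstructured model. 0.24 / 6.6 is 3.6% of the target difference.

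**The case against.** The protocol says random intercepts will be fitted; it does not say that residuals are independent with equal variance, and section 12.2 leaves detail to a SAP. That SAP could add robust standard errors without contradicting section 12.5.1. This is fair as far as it goes. But the protocol names a covariance structure and stops there, so this is a stated choice and not silence. Taken as written, it gives the pooled variance.

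It is also fair that modelling all time points is legitimate and serves the month-9 and month-12 outcomes, and that a steady fall in SD leaves the level close to nominal.

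Three stronger readings are tempting and not supported:

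- **That the error rate is inflated.** The documents give no SD except at 24 weeks. Inflation needs month 6 to be more variable than the five-visit average; if it is less variable, the test is conservative.
- **That post-switch data bias the month-6 estimate.** With complete data and an arm-by-time interaction, the point estimate is essentially unaffected; it is the variance that is pooled.
- **That the missing-at-random claim in section 12.10 fails materially.** Likelihood validity does need a correct covariance, but the one bias figure available is small and comes from a constructed scenario. Months 9 and 12 can inform a missing month-6 value only for participants who miss month 6 and return, not for those already lost.

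**Conclusion.** The point holds as a weakness in a stated method. As written, the primary interval and test have their nominal properties only if the month-6 residual variance equals the average over five visits, and the protocol gives no support for that equality. Under the assumed patterns the actual level runs from about 1.6%, through near nominal, to about 4% when only the post-switch SDs narrow, and 5 to 6% when month 6 is the most variable visit. These figures depend on assumed SDs with month 6 fixed at 13.6, so the direction for this trial is unknown. The right description is that 0.025 is not guaranteed, not that it is exceeded. Effects on the point estimate are absent or small. Because a better method costs almost nothing, the change should be made.

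**What to change.** In section 12.5.1, replace the lone random intercept with an unstructured covariance across visits (visit-specific variances and correlations) and add a baseline EASI by visit term. Alternatively, keep the model and report participant-clustered robust standard errors. Name the robust version as the fallback if the unstructured model does not converge. Since section 12.5.2 uses the same approach, the change should carry over to the continuous secondary outcomes.

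Limiting the primary model to visits up to month 6 is optional; it keeps post-switch data out of the primary test but does not replace the covariance change.

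The cost is protocol or SAP wording, a few more variance parameters and a small convergence risk, which the fallback covers. Sample size and data collection do not change.

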12.5.2 STATISTICAL METHODS FOR SECONDARY OUTCOMES

For continuous secondary outcomes, the same modelling approach will be followed as for the primary outcome.

For binary secondary outcomes logistic mixed models will be estimated. We will report the treatment effect estimate as the conditional odds-ratio, the 97.5% confidence interval and p-value.

12.6 INTERIM ANALYSES (STATISTICAL)

Following discussion with the oversight groups, sponsor and funder as the study progresses, we may include one interim analysis for futility and efficacy. This will control the type 1 error rate for each pairwise comparison and have minimal impact on the power for the final analyses.

12.7 INTERNAL PILOT 'GO'/'NO GO' PROGRESSION

The initial 10 months of recruitment forms the internal pilot phase, to enable NIHR HTA to confirm progression criteria are met.

12.8 METHODS TO ACHIEVE TARGET SAMPLE SIZE

Trial recruitment will be monitored closely by the Trial Manager and reported at the TMG meetings. Anonymised participant pre-screening logs will be requested from sites and assessed on an ongoing basis. Section 5.2 outlines how participants will be identified for inclusion in the trial.

Additionally, the KCTU Standard Operating Procedures (SOPs) will guide the Trial Statistician's reports outlining recruitment numbers across the trial and at site level to the DMC. The DMC will be asked to advise on strategy where there are recruitment difficulties i.e., including but not limited to; modifications to the inclusion/exclusion criteria, targeted recruitment drives, escalation at site level to PI/R&D or site closure.

12.9 METHODS FOR ADDITIONAL ANALYSES (E.G. SUBGROUP ANALYSES)

For subgroup analysis (moderate and severe groups), treatment effect estimates will be estimated for each subgroup and formally tested by including an interaction between subgroup and treatment as a fixed effect in the analysis models.

In a secondary analysis, to identify the optimal treatment pathways adjusting for non-responders who switch treatments, we will use Q-learning to identify the pathway that maximises the expectation of the outcomes at 12 months, and if these differ by patient characteristics. Q-learning is a popular, regression-based approach for estimating treatment pathways involving treatment switching over time, as is permitted in this study after 6 months for non-responders. It involves defining the quality of treatment functions (Q-functions) at each time point. For the clinician-assessed eczema severity (EASI) outcome at 1 year, this is the expectation of the outcome conditional on treatment and covariate history from 6 months and baseline, estimated through linear regression. The maximum argument of the expectation with respect to the choice of treatments at 6 months is then regressed on the baseline randomisations and covariates. The optimal treatment pathway for an individual is then defined as the pathway that maximises the Q-function at both time points, and this will be estimated for different subgroups of participants.

We will additionally explore whether the carriage of filaggrin-null mutations, baseline IgE and eosinophils and predominant head and neck eczema predicts treatment response on the three treatments and whether methotrexate polyglutamate measurement can be used as a biomarker for treatment response in those on methotrexate.

If two comparators (A, B) are both found to be superior to the current control (C) in each respective pair-wise comparison, we may make a direct comparison between A and B. There is limited power for such a comparison, and the results of this direct comparison will be presented as opportunistic and exploratory. Only participants that could have been randomised to both A and B will be included in this opportunistic comparison (i.e., will exclude participants that were contraindicated to 1 or both arms, and will exclude participants that were randomised when 1 arm was not yet available).

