2 TRIAL DESIGN

This is a UK, multicentre, one year, assessor-blind, randomised controlled trial assessing systemic treatments in adults with moderate to severe eczema. Three mechanistic classes of drugs are being tested against a control (ciclosporin). Further treatments and arms may be added in future amendments.

Participants will be randomised in a 1:1:1:1 ratio. **During the first stage of the trial (months 1-6)**, **follow up will be face to face at 1, 3 and 6 months** for safety and effectiveness assessment (see Figure 2 for trial flow diagram and Table 1 for schedule of events). There are additional drug-specific safety only visits for some arms as shown in Table 1, Figure 2, and individual flow diagrams in drug specific Appendices 1-4, in line with routine care and national guidance. There is the **option to increase the treatment dose at 3 months for some arms if there has been an inadequate response** following which additional safety only visits may be required (see Table 1 schedule of events, Figure 2 trial flow diagram, and individual flow diagrams in drug specific appendices 1-4). Dose reduction will be permitted at any stage as clinically indicated and according to standard clinical practice. Safety only visits (when no additional effectiveness measure is conducted) can be conducted in the community where deemed appropriate by the investigator (general practice). If participants attend study sites, contact with study staff should be minimised and staff will be trained to not provide additional support to minimise performance bias.

The primary outcome will be assessed at 6 months. Responders, defined as those achieving at least a 50% improvement in the objective EASI score (EASI50) and $a \ge 4$ point reduction in Dermatology Life Quality Index (DLQI) will continue the same therapy for a further 6 months (up to 1 year) if they are tolerating the treatment and are happy to continue (in line with NICE guidance (NICE TA534¹⁷)). Non-responders will switch therapy in a pre-determined way that mirrors real world practice (see Figure 2).

In the second stage of the trial (months 7-12) face to face safety and effectiveness assessments will be at 9 and 12 months. For those participants who have switched therapy there will be an additional telephone/ remote safety only visit (with bloods) at 7 months. Dependent upon

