6.4.1 OBJECTIVE MEASURES (BLINDED ASSESSOR)

6.4.1.1 ECZEMA AREA AND SEVERITY INDEX (EASI)

The EASI is an objective disease severity score that assesses clinical signs in eczema across four body sites (arms, face/neck, trunk, legs) including erythema, induration, excoriation, lichenification (each on a 4 point scale) as well as area of involvement, with a maximum score of 72. This will be assessed by a nominated blinded-assessor at site. Site staff will only be delegated to complete this assessment if they have completed the relevant training and are certified to complete the assessments. If the investigator feels that there is a temporary confounding skin condition that will significantly affect the ability to obtain an accurate EASI (e.g. severe sunburn) then they should defer the visit / blinded assessment as appropriate, within the visit window where at all possible (see section 6.1.1).

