7 INTERVENTIONS

7.1 CHOICE OF COMPARATORS

In the first iteration of the platform two different classes of systemic therapy (methotrexate and dupilumab) were tested against a control (ciclosporin). Abrocitinib is the first new treatment arm to enter the platform and has been included as an exemplar of the new class of JAK inhibitors licensed for and increasingly used to treat adult atopic eczema.

Further treatments and arms will be added in future amendments. The Trial Management Group (TMG) are responsible for proposing those treatments and related dosing to the Trial Steering Committee (TSC) for ratification.

Patients will be randomised 1:1:1:1 to one of the following trial arms:

- 1. Ciclosporin (PO)
- 2. Methotrexate (SC)
- 3. Dupilumab (SC)
- 4. Abrocitinib (PO)

For detailed information on each IMP please refer to the relevant individual drug appendix (Appendices 1-4). Information regarding side effects and administration is provided in those appendices and in the Participant Information Sheet (PIS).

7.2 INTERVENTION AND COMPARATOR DESCRIPTION, DOSING, PACKAGING, LABELLING, STORAGE AND ACCOUNTABILITY

Sites should not randomise patients unless they have sufficient drug available on site for all trial arms.

Investigators will be encouraged to adhere to the suggested dose increases for ciclosporin and methotrexate, but changes of dose outside of this schedule where clinically indicated will be permitted and recorded.

Dispensed trial medicines will be collected from pharmacy by the patient or their representative. At the baseline visit, the research team will train the patient on how to administer their new treatment using either their dispensed medication or a dummy device and counsel them on the new medication.

Participants should start the medication the day of their baseline visit, but if that is not possible as soon as possible thereafter. If there is a delay of more than 2 weeks then the site must contact the BEACON team to clarify how to proceed.

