1.1.4 RATIONALE FOR 6 MONTH SWITCH OPTION FROM CICLOSPORIN (DUPILUMAB)

For those participants on ciclosporin who do not meet response criteria to continue at 6 months they can switch to dupilumab. Dupilumab was chosen as the switch option to most closely mirror clinical practice (in line with NICE TA534).

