1.1.4 RATIONALE FOR 6 MONTH SWITCH OPTION FROM METHOTREXATE (DUPILUMAB)

For those participants on methotrexate who do not meet response criteria to continue at 6 months they can switch to dupilumab. Dupilumab was chosen as the switch option to most closely mirror clinical practice (in line with NICE TA534).

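### Section 12.9 optimises over a month-6 treatment choice that the design does not contain, and maximises expected EASI although a higher score is worse

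*Protocol*

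**What the plan says.** Section 12.9 presents Q-learning as a secondary analysis to find the best treatment pathway, allowing for the switching of non-responders. For EASI, the Q-function is the expected one-year score given treatment and covariate history, fitted by linear regression. The second-stage step is "The maximum argument of the expectation with respect to the choice of treatments at 6 months", which is then regressed on the baseline allocation and covariates. The decision rule is "The optimal treatment pathway for an individual is then defined as the pathway that maximises the Q-function at both time points".

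The design sections describe something narrower. Section 7.1: "Patients will be randomised 1:1:1:1 to one of the following trial arms". No later randomisation is described. Under section 2, responders "will continue the same therapy for a further 6 months (up to 1 year) if they are tolerating the treatment" (and wish to go on), while "Non-responders will switch therapy in a pre-determined way that mirrors real world practice". The appendices name one switch per arm. Appendix 1 has "For those participants on ciclosporin who do not meet response criteria to continue at 6 months they can switch to dupilumab", and Appendix 2 has "For those participants on methotrexate who do not meet response criteria to continue at 6 months they can switch to dupilumab". Section 1.1.4 of Appendices 3 and 4 names methotrexate as the switch from dupilumab and from abrocitinib. Section 5.3.3 withdraws participants whose named switch is not possible.

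Section 6.4.1.1 describes EASI as a severity score built from clinical signs "as well as area of involvement, with a maximum score of 72". Section 2 defines response as an improvement in it.

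**The concern.** Q-learning compares second-stage treatments among people who share a history. If everyone with a given history is assigned the same treatment, the data carry no designed information on any alternative. A linear regression will still return a best month-6 treatment if asked. It does so by borrowing effects from other arms, or from participants who departed from the plan at their own or the investigator's discretion (section 7.3). Neither source is randomised.

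The direction is a separate fault. The rule maximises the expectation of an outcome that section 12.9 itself labels as severity, and no reversal of sign is stated.

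What is at stake is interpretation. Section 1.2 lists the lack of evidence on the best pathway after a switch as a gap that the trial addresses. A reported optimal pathway could therefore be read as evidence on which second-line drug to choose, which this design does not supply.

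**Working it through.** The plan gives no figure for this analysis, so there is none to reproduce. The check is structural.

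**Step 1: list the month-6 options.** Sources are section 2 and section 1.1.4 of Appendices 1 to 4.

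| Randomised arm | Responder | Non-responder |
|---|---|---|
| Ciclosporin | ciclosporin | dupilumab |
| Methotrexate | methotrexate | dupilumab |
| Dupilumab | dupilumab | methotrexate |
| Abrocitinib | abrocitinib | methotrexate |

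Histories: 4 arms × 2 response states = 8. Assigned options per history: 1. Histories with two or more options: 0.

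**Step 2: is a second-stage contrast estimable?** Take a regression with 8 history indicators plus 8 products of history and switching (yes or no), 16 columns in all. In the 4 responder histories nobody switches, so those product columns are all zero. In the 4 non-responder histories everybody switches, so each product column duplicates its history indicator. The rank is therefore 8, not 16. A simulated data set of 107 per arm (134 × 0.8 ≈ 107, the planned size after 20% loss) confirmed this: 16 columns, rank 8. No within-history treatment effect can be estimated, and a larger sample would not change that.

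**Step 3: what the procedure becomes when only assigned options are allowed.** Write Y for EASI at 12 months, H for the history at month 6, X for baseline covariates and A for the randomised arm. Section 12.9's second-stage quantity is read here as the optimised value.

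- Stage 2: Q2(h, a) = E[Y | H = h, month-6 treatment = a].
- Optimised value: V(h) = the best Q2(h, a) over the allowed a.
- With one allowed treatment per history, V(h) = E[Y | H = h], whether one maximises or minimises.
- Stage 1: Q1(x, a) = E[V(H) | X = x, A = a] = E[Y | X = x, A = a].

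The last line is the ordinary regression of 12-month EASI on randomised arm and baseline covariates. It is identified by the baseline randomisation and compares four strategies: each starting drug together with its fixed switch for non-response.

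**Step 4: direction.** The optimisation that remains is over A. Choosing the arm with the largest E[Y | X, A] chooses the highest expected severity, by definition. Using change from baseline as follow-up minus baseline does not help, because its largest value is the smallest improvement. An illustrative simulation with assumed drug and switch effects gave arm means between 8.6 and 10.7. The literal rule picked 10.7 and the reversed rule picked 8.6. Those values show direction only and do not predict results.

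**The case against.** The strongest reply is that the analysis survives. Secondary objective 5 (section 3.2) asks only about pathways under test. Q-learning does not require two treatments per history: it requires support for whatever is allowed, and a single allowed option is degenerate but valid. Section 12.9 links switching to what the trial permits non-responders to do, and it ends with a regression on the baseline allocation. Read that way, it is the identified comparison in step 3. This stands, and it limits the point.

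A reader might infer that section 12.9 cannot answer objective 5 at all, or that nothing else in the protocol bears on it. The documents support neither. EASI change at month 12 is a secondary outcome (section 4.2), analysed by the same mixed model as the primary (section 12.5.2), by randomised arm and among participants eligible for and concurrently randomised to both arms (section 12.3). Because switching follows a fixed rule, that contrast already compares much of each strategy with ciclosporin.

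On direction, it can be said that maximising is the textbook form and is right for response proportions or for EASI reduction. That is fair, and a careful analyst would probably notice. But the outcome that section 12.9 names is one-year EASI severity, so the written rule is still wrong.

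Nor is this detail that can simply be left to the SAP. The protocol itself fixes the outcome, the regression and the optimisation step, and these conflict with its own design and outcome definition.

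**Conclusion.** Wrong as written, of moderate severity. Section 12.9 describes a month-6 choice that none of the 8 histories contains, and it optimises EASI in the wrong direction. The best of the four tested strategies, overall or by baseline characteristics, remains answerable. The best second drug for a given non-responder, and whether a responder should switch, are not. The primary analysis, sample size and error control are untouched.

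The conclusion rests on three assumptions. The trial flow figure is not shown, so the switch routes come from the appendices. The appendices' permissive wording (participants can switch) is taken to allow declining, not to offer a second designed option; likewise, responders who stop are treated as non-randomised departures. Identification of the month-12 comparison is subject to the usual missing-data assumptions, including for participants withdrawn because their switch was not possible.

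**What to change.** In section 12.9:

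- Restrict the month-6 options to the treatment that the protocol assigns for each arm and response state. State the analysis as a month-12 comparison of the four randomised strategies (starting drug plus its fixed switch).
- Explore tailoring with baseline characteristic by randomised arm terms.
- Restrict each comparison to participants eligible for, and concurrently randomised between, the arms compared, as section 12.3 already requires.
- State that switches the trial does not assign are not estimated.
- Define the optimum as minimising expected EASI, or as maximising EASI reduction. Give the direction for any other outcome analysed this way.

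The cost is a wording change in the protocol, carried into the SAP, and a simpler analysis. The downside is that the trial makes no claim about switches that it never assigns.
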